### 12.7 Eastern Cooperative Oncology Group (ECOG) Performance Status

Shift of ECOG from baseline to the worst score during the treatment will be summarized in a shift table.

### 12.8 Electrocardiogram (ECG)

ECG will be done in triplicate ( $\geq 1$  minute apart) at screening for all subjects. The intensive ECG schedule as specified in the Schedule of Assessments of the protocol is only for the subjects in the dose escalation portion of the study. The intensive ECG data analysis will be performed by an Acerta designated vendor and a separate detailed report will be included as part of the CSR.

### **13.0 DEVIATIONS FROM PROTOCOL AND OTHER ISSUES**

Time to initial response is not specified as an efficacy endpoint in the protocol. Since it provides information about the onset of response, it is added to the SAP as an efficacy endpoint.

If there are changes to the planned analyses described in the SAP, they will be described in the clinical study report.

### **15.0 APPENDICES**

# **Appendix A: Analysis Windows**

Tumor assessment/CT/SPD					
			Analysis Window (Study Day)		
Nominal Visit	Study Day	Nominal Month	Lower (inclusive)	Upper (inclusive)	
C2D28	56	2	2	84	
C4D28	112	4	85	140	
C6D28	168	6	141	210	
C9D28	252	8	211	294	
C12D28	336	11	295	378	
C15D28	420	14	379	462	
C18D28	504	17	463	546	
C21D28	588	19	547	630	
C24D28	672	22	631	756	
C30D28	840	28	757	924	
C36D28	1008	33	925	1092	
C42D28	1176	39	1093	1260	
C48D28	1344	44	1261	1428	
C54D28	1512	50	1429	1596	
C60D28	1680	55	1597		

Hematology / Chemistry					
			Analysis Window (Study Day)		
Nominal Visit	Study Day	Nominal Month	Lower (inclusive)	Upper (inclusive)	
C1D1	1	0		1	
C1D28	28	1	2	42	
C2D28	56	2	43	70	
C3D28	84	3	71	98	
C4D28	112	4	99	126	
C5D28	140	5	127	154	
C6D28	168	6	155	210	

CONFIDENTIAL

C9D28	252	8	211	294
C12D28	336	11	295	378
C15D28	420	14	379	462
C18D28	504	17	463	546
C21D28	588	19	547	630
C24D28	672	22	631	714
C27D28	756	25	715	798
C30D28	840	28	799	882
C33D28	924	30	883	966
C36D28	1008	33	967	1050
C39D28	1092	36	1051	1134
C42D28	1176	39	1135	1218
C45D28	1260	41	1219	1302
C48D28	1344	44	1303	1386
C51D28	1428	47	1387	1470
C54D28	1512	50	1471	1554
C57D28	1596	52	1555	

Amylase / Lipase					
			Analysis Window (Study Day)		
Nominal Visit	Study Day	Nominal Month	Lower (inclusive) Upper (inclusive)		
C1D1	1	0		1	
C1D28	28	1	2	42	
C2D28	56	2	43	70	
C3D28	84	3	71	98	
C4D28	112	4	99	126	
C5D28	140	5	127	154	
C6D28	168	6	155	210	
			Last dose	Last dose	
SFU			date +15	date +45	

Serum Ig, T cell (CD4, CD8), NK and monocyte						
	counts					
			Analysis Window			
			(Study	y Day)		
Nominal Visit	Study Day	Nominal Month	Lower (inclusive)	Upper (inclusive)		
C1D1	1	0		1		
C2D28	56	2	2	154		
C9D28	252	8	155	336		
C15D28	420	14	337	504		
C21D28	588	19	505	672		
C27D28	756	25	673	840		
C33D28	924	30	841	1008		
C39D28	1092	36	1009	1176		
C45D28	1260	41	1177	1344		
C51D28	1428	47	1345	1512		
C57D28	1596	52	1513			

B Symptoms				
			Analysis Window (Study Day)	
Nominal Visit	Study Day	Nominal Month	Lower (inclusive)	Upper (inclusive)
C1D1	1	0		1
C2D15	43	1	2	64
C3D28	84	3	65	98
C4D28	112	4	99	126
C5D28	140	5	127	154
C6D28	168	6	155	210
C9D28	252	8	211	294
C12D28	336	11	295	378
C15D28	420	14	379	462
C18D28	504	17	463	546
C21D28	588	19	547	630
C24D28	672	22	631	714
C27D28	756	25	715	798
C30D28	840	28	799	882
C33D28	924	30	883	966

CONFIDENTIAL

C36D28	1008	33	967	1050
C39D28	1092	36	1051	1134
C42D28	1176	39	1135	1218
C45D28	1260	41	1219	1302
C48D28	1344	44	1303	1386
C51D28	1428	47	1387	1470
C54D28	1512	50	1471	1554
C57D28	1596	52	1555	

### Appendix B: Rai Stage Derivation Criteria

Stage	Lymphocytosis	Lymphadenopathy	Hepatomegaly or splenomegaly	Anemia	Thrombocytopenia
0	1	0	0	0	0
Ι	1	1	0	0	0
II	1	any	1	0	0
III	1	any	any	1	0
IV	1	any	any	any	1

1 = yes, 0 = no, any = yes or no

	Decrease in platelets  or Hb  (nadir) from	Absolute neutrophil
Grade 	pretreatment value	$count/\mu L^4$ (nadir)
0	No change to 10%	≥2000
1	11%-24%	$\geq 1500 \text{ and } \leq 2000$
2	25%-49%	$\geq 1000 \text{ and } < 1500$
3	50%-74%	$\geq$ 500 and <1000
4	≥75%	<500

### Appendix C: Grading Scale for Hematologic Toxicity in CLL (Hallek 2008)

1. Grades: 1, mild; 2, moderate; 3, severe; 4, life-threatening; 5, fatal. Death occurring as a result of toxicity at any level of decrease from pretreatment will be reported as Grade 5.

[figure not shown]
Platelet counts must be below normal levels for Grades 1 to 4. If, at any level of decrease, the platelet count is <20 x 10^9/L (20,000/μL), this will be considered Grade 4 toxicity, unless a severe or life-threatening decrease in the initial platelet count (eg, <20 x 10^9/L [20,000/μL]) was present pretreatment, in which case the patient is not evaluable for toxicity referable to platelet counts.

3. Hemoglobin (Hb) levels must be below normal levels for Grades 1 to 4. Baseline and subsequent Hb determinations must be performed before any given transfusions. The use of erythropoietin is irrelevant for the grading of toxicity, but should be documented.

4. If the ANC reaches <1 x 10^9/L (1000/µL), it should be judged to be Grade 3 toxicity. Other decreases in the white blood cell count, or in circulating neutrophils, are not to be considered because a decrease in the white blood cell count is a desired therapeutic endpoint. A gradual decrease in granulocytes is not a reliable index in CLL for stepwise grading of toxicity. If the ANC was <1 x 10^9/L (1000/µL) before therapy, the patient is not evaluable for toxicity referable to the ANC. The use of growth factors such as granulocyte colony-stimulating factor (G-CSF) is not relevant to the grading of toxicity, but should be documented.

### **Appendix D: Defining Prior and Concomitant Medication Flags**

The figure below depicts various scenarios of prior and concomitant medications. The prior and concomitant medication flags are specified respectively for each scenario.

### Appendix E: Definition of Adverse Event of Special Interest and Events of Clinical Interest (MedDRA version 24.0)

### 1. Adverse Event of Special Interest (AESI)

The following preferred terms (PT) for the ventricular arrhythmias AESI include:

- Torsade de pointes
- Ventricular arrhythmia
- Ventricular extrasystoles
- Ventricular fibrillation
- Ventricular flutter
- Ventricular tachyarrhythmia
- Ventricular tachycardia

### 2. Events of Clinical Interest

The Events of Clinical Interest (ECIs) have been identified based on preclinical findings, emerging data from clinical studies relating to acalabrutinib, and pharmacological effects of approved Bruton's tyrosine kinase (BTK) inhibitors. The adverse events (AEs) selected for dedicated analysis were evaluated using Standardized MedDRA Queries (SMQs), where available, by System Organ Classes (SOCs), or by Sponsor-defined baskets of MedDRA Adverse Event Grouped Terms.

Category	Subcategory	Definition
Cardiac events		SOC Cardiac disorders
	Atrial fibrillation	PT Atrial fibrillation
		PT Atrial flutter
	Ventricular	PT Torsade de pointes
	tachyarrhythmias	PT Ventricular fibrillation
		PT Ventricular flutter
		PT Ventricular tachyarrhythmia
		PT Ventricular tachycardia
Cytopenias –		• SMQ Haematopoietic erythropenia [narrow +
Anemia		broad]
Cytopenias –		• SMQ Haematopoietic leukopenia [narrow +
Leukopenia		broad]
	Neutropenia	
 
PT Band Neutrophil count decreased
 

		• PT Band neutrophil percentage decreased
		PT Cyclic neutropenia
		PT Febrile Neutropenia
		PT Idiopathic neutropenia
		PT Neutropenia
		PT Neutropenic infection
		PT Neutropenic sepsis

CONFIDENTIAL

1		
		PT Neutrophil count decreased
		PT Neutrophil percentage decreased
	Other leukopenia	
 
SMQ Haematopoietic leukopenia [narrow + broad] excluding PTs for neutropenia above
 

Cytopenias - Thrombocytopenia		
 
SMQ Haematopoietic thrombocytopenia [narrow + broad]
 

Hemorrhage		• SMQ Haemorrhage terms (excl laboratory terms)
	Major hemorrhage	• As per definition (see Section 3 below)
Hepatotoxicity		• SMQ [narrow] Hepatic failure, fibrosis and cirrhosis and other liver damage-related conditions
		• SMQ [narrow] Hepatitis, non-infectious
		• SMQ [narrow] Liver related investigations
II		signs
Hypertension		SMQ Hypertension [narrow]
Infections		SOC Infections and infestations
Interstitial lung disease/Pneumonitis		• SMQ [narrow] Interstitial lung disease
Second primary malignancies	Second animary	
 
SMQ Malignant tumours (including Haematological malignant tumours SMQ and Non-haemoatological malignant tumours SMQ)
 
SMQ Malignant lymphomas [narrow] SMQ Myelodysplastic syndrome [narrow]
 

	Second primary malignancies (excluding non melanoma skin)	• The above excluding PTs mapping to HLT Skin neoplasms malignant and unspecified (excluding melanoma)
Tumor lysis syndrome		PT Tumour lysis syndrome

HLT=High-Level Term; PT=Preferred Term; SOC=System Organ Classes; SMQ=Standardized MedDRA Queries.

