# **1.0 INTRODUCTION**

This statistical analysis plan (SAP) provides details of the statistical analyses that have been outlined within the protocol for study ACE-CL-001 Protocol Amendment 13 (dated August 25th, 2021), which is entitled "A Phase 1/2, Multicenter, Open-label, and Dose-escalation Study of ACP-196 in Subjects with Chronic Lymphocytic Leukemia, Richter's Syndrome or Prolymphocytic Leukemia". From here on, acalabrutinib will be used in place of ACP-196 in this document.

The scope of the SAP will cover safety and efficacy analyses. Pharmacokinetic (PK) and pharmacodynamic (PD) analyses will be provided in the respective reports. Analysis of electrocardiogram (ECG) data will be performed by an Acerta designated vendor and a separate detailed report will be included to the interim Clinical Study Report (CSR).

If there are differences between protocol specified analyses and the SAP, the SAP will supersede protocol. Major differences will be noted and rationale will be provided in Section 13.0 of this document and the interim CSR.

To support the acalabrutinib New Drug Application (NDA) for relapsed or refractory Mantle Cell Lymphoma (MCL) in 2017, an interim CSR of study ACE-CL-001 was provided consisting of safety analyses for all disease subgroups and efficacy analyses for the relapsed or refractory (RR) disease subgroup as assessed by the investigator. Independent Review Committee (IRC) assessment was not available at this time and was not included in the interim CSR per Protocol Amendment 8 (dated 08 January 2016).

To support the acalabrutinib supplemental New Drug Application (sNDA) for previously untreated and relapsed or refractory chronic lymphocytic leukemia (CLL) in 2019, an interim CSR of study ACE-CL-001 with updated datasets was provided consisting of safety analyses and efficacy analyses for the treatment naïve (previously untreated) and relapsed or refractory (RR) disease subgroup as assessed by the investigator. The requirement of IRC assessment of response was removed in Protocol Amendment 10 (dated 22 February 2018).

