### 9.0 DEMOGRAPHICS AND BASELINE DISEASE CHARACTERISTICS

The following variables collected at baseline will be presented:

- Demographics
  - Age (years)
    - Descriptive statistics
    - o <65 vs. ≥65 years

- $\circ$  <70 vs.  $\geq$ 70 years
- Sex (male, female)
- Race
  - American Indian/Alaskan Native, African American/Black, Asian, Caucasian/White, Native Hawaiian/Other Pacific Islander or Other
  - White vs. Non-white
- Ethnicity (Hispanic or Latino, Non-Hispanic or Latino)
- Enrollment by region (United States, Ex-United States)
- Baseline disease characteristics
  - Height
  - Weight
  - Histology
    - For RR, TN, ibrutinib intolerant, and ibrutinib relapse/refractory
      - CLL
      - SLL
    - For RS/PLL
      - CLL transformed to DLBLC
      - CLL transformed to PLL
      - FL transformed to DLBCL
  - Time since initial CLL diagnosis to first dose (years) (not applicable to RS/PLL)
  - Time since initial CLL diagnosis to transformation (years) (RS/PLL only)
  - Time since transformation to first dose (years) (RS/PLL only)
  - ECOG performance status
  - Chromosomal abnormalities
    - Deletion 17p: 17p13 (TP53)
    - Deletion 11q: 11q22.3 (ATM)
    - Unmutated IGHV
  - β2-microglobulin
    - $\circ$  >3 vs.  $\leq$ 3 mg/L
    - $\circ \quad >3.5 \ vs. \leq 3.5 \ mg/L$

- Bulky disease (not applicable for RS/PLL) defined as if at least one dimension of the lymph node measurement is
  - $\circ \geq 5 \text{ cm}$
  - $\circ \geq 10 \text{ cm}$
- Rai stage derived based on variables collected at screening visit using the criteria described in Appendix B. Additionally, Rai stage collected on the eCRF will be summarized. Rai stage is not applicable to RS/PLL cohort.
- B symptom weight loss, fever, night sweats
- Number of prior systemic therapy
  - Descriptive statistics
  - $\circ$  <3 vs.  $\geq$ 3
- Type of prior systemic therapy
- Time since most recent systemic therapy (months)
- Cytopenia
  - Absolute neutrophil count (ANC)  $\leq 1.5 \times 10^{9}/L$
  - $\circ$  Hemoglobin  $\leq 11g/dL$
  - $\circ$  Platelet  $\leq 100 \times 10^{9}/L$
  - Hemoglobin  $\leq 11g/dL$  or platelet  $\leq 100x10^9/L$
  - Any of the above
- ANC (10^9/L)
  - Descriptive statistics
  - $\circ$  ANC >1.5 to <2 x10^9/L
- Absolute lymphocyte count (ALC) (10^9/L)
- Hemoglobin (g/dL)
- Platelets  $(10^{9}/L)$
- Sum of product diameter (SPD) (cm^2)
- Baseline hepatomegaly per PE
- Baseline splenomegaly per PE

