#### 2. Additional Criteria for Narratives:

• Subjects who fulfill ECI (see Appendix 1 for definitions) criteria and additional criteria for narratives as described below:

Note: the window for qualifying events for narratives is from first date of study drug to last date of study drug + 30 days. Beyond this window, narratives should also be provided for any related SAEs and for clinically significant AEs as judged by medical monitor.

ECI Category Name	ECI Subcategory Name	Additional Criteria for Narratives
Cardiac events	Atrial fibrillation	Grade 3 and 4 PT Atrial fibrillation
		• Grade 3 and 4 PT Atrial flutter
Hemorrhage	Major hemorrhage	Same as ECI definition. Refer to Appendix 1 Section 2
Hepatotoxicity		Subjects who fulfill biochemical Hy's law criteria defined as below: $\geq 3 \times ULN \text{ AST or}$ $\geq 3 \times ULN \text{ ALT and}$ $\geq 2 \times ULN \text{ total bilirubin}$ where bilirubin increased of $\geq 2xULN$ either coincides with ALT/AST elevations or follow them within 8 days
Second primary malignancies	Second primary malignancies (excluding non melanoma skin)	
 
Below SMQs excluding PTs mapping to HLT Skin neoplasms malignant and unspecified (excluding melanoma)
 
SMQ Malignant tumours (including Haematological malignant tumours SMQ and Non- haemoatological malignant tumours SMQ
 
SMQ Malignant lymphomas [narrow]
 
SMQ Myelodysplastic syndrome [narrow]
 

Tumor lysis syndrome		Same as ECI definition. Refer to Appendix 1 Section 2

AE=adverse event; ALT=alanine aminotransferase; AST=aspartate aminotransferase; HLT=high-level term; ISS=integrated safety summary; PT=preferred term; SAE=serious adverse event; SMQ=Standardised MedDRA Query; ULN=upper limit of normal.

MedDRA version 24.0

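### The second-primary-malignancy definition has no step separating a new primary from the study disease or its transformation, so an AE coded to such a leukaemia or lymphoma term counts as a second primary

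*SAP*

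**What the plan says.** SAP Appendix E, Section 2 (Events of Clinical Interest), builds the second-primary-malignancy category from three queries. The first is "SMQ Malignant tumours (including Haematological malignant tumours SMQ and Non-haemoatological malignant tumours SMQ". The second is "SMQ Malignant lymphomas [narrow" scope, and the third is the myelodysplastic syndrome query, also at narrow scope.

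The appendix then gives a subcategory with one exclusion: "The above excluding PTs mapping to HLT Skin neoplasms malignant and unspecified (excluding melanoma". The parent category has no exclusion.

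Appendix F, under the additional criteria for narratives, repeats the search for the subcategory with the same single exclusion: "Below SMQs excluding PTs mapping to HLT Skin neoplasms malignant and unspecified (excluding melanoma".

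The trial's title, given in SAP Section 1.0, describes the population as "Subjects with Chronic Lymphocytic Leukemia, Richter's Syndrome or Prolymphocytic Leukemia". Section 9.0 lists among the baseline histologies of the RS/PLL group "CLL transformed to DLBLC" (a misprint for DLBCL).

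Section 12.1 defines treatment-emergent AEs by timing only: from first dose to 30 days after the last dose. For the definition of each event of clinical interest it refers to Appendix B of the Integrated Summary of Safety, not to the SAP's own Appendix E.

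**The concern.** The label says second primary, but the rule selects any malignancy term within the queries. In most oncology trials that matters little, because a solid-tumour study disease is easily told apart from a haematological hit. Here the study disease is itself a leukaemia or lymphoma, and its known transformation is to a lymphoma. The search has no means of telling the first malignancy from a second one.

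Two things are at stake. First, the reported second-primary rate could be inflated by events that are disease progression. The same event could then count as progression in the PFS analysis of Section 11.2 and again as a second primary in the safety tables. Second, a programmer following Appendix E has no written basis for removing such hits. Any removal would be an unplanned decision taken with the data in view.

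**Working it through.** The SAP states no figure for this category, so there is none to reproduce. The check is a reading of every place that defines, filters or reuses the category, followed by simple arithmetic for scale.

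**Is there an exclusion anywhere in the SAP?**

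| Place in SAP | What it contributes | Removes study-disease hits? |
|---|---|---|
| Appendix E, Section 2, parent category | Three queries, haematological tumours expressly included | No |
| Appendix E, Section 2, subcategory | Same queries less non-melanoma skin | No |
| Appendix F, additional narrative criteria | Same queries less non-melanoma skin | No |
| Section 12.1, treatment-emergent AE | Timing window only | No |
| Section 12.1, event-of-clinical-interest reference | Points to Integrated Summary of Safety, Appendix B | Not at hand |

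No place requires medical confirmation that a hit is a new primary.

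**Could the omission be house style, with exclusions left implicit?** Appendix E writes exclusions out where it wants them. The other-leukopenia row removes terms already counted elsewhere ("excluding PTs for neutropenia above"), and the second-primary subcategory removes skin terms. Silence on the study disease therefore reads as no exclusion.

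**Scale per misclassified subject.** Inputs are the planned sizes in Section 4.0 and its Table 2. Section 6.1 says tables are presented by disease subgroup and cohort, so the cohort denominators matter. The added rate is 1/N.

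- All subjects, N = 286 (approximate, planned): 1/286 = 0.35 percentage points.
- A 30-subject cohort, such as Cohort 9 (RS/PLL): 1/30 = 3.3 points.
- Cohort 2b, N = 65: 1/65 = 1.5 points.

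The total inflation is the number of misclassified subjects divided by N. The SAP gives no such number. Any assumed percentage of subjects would simply come back as the same number of percentage points, so none is offered here.

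**The case against.** The strongest reply is that the search acts only on AE records. Whether progression or transformation is recorded as an AE is a reporting rule that normally sits in the protocol, which is not at hand. The SAP treats documented progression as a PFS event, and nothing in it shows that progression also enters the AE data. This stands: the effect may be zero, and the point is conditional on such events being recorded.

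Second, the SAP does not list the terms inside the queries. It is a fair reading of their names that they reach leukaemia and lymphoma terms, but an event coded to a general disease-progression term might fall outside. The lymphoma query is also restricted to narrow scope, so not every lymphoma term is necessarily captured. This also stands, and it limits the point to events coded to terms within the queries.

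Third, Section 12.1 refers to a definition in the Integrated Summary of Safety, which might contain an exclusion or a review step. That leaves some uncertainty. But Appendix E is titled as the definition and has neither. If the two sources differ, the SAP rests on two definitions.

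Fourth, the consequence is bounded. Section 6.1 rules out formal hypothesis tests. Appendix F already calls for narratives on all deaths, including those from progressive disease, on other SAEs and on AEs leading to discontinuation. The narrative effect is therefore mostly some extra narratives.

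A reader might also infer from the baseline histologies in Section 9.0 that the whole RS/PLL cohort would be counted as second primaries. The SAP does not support that. Disease present at entry is not treatment-emergent under Section 12.1, and only a new AE record after first dose could be picked up.

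**Conclusion.** The point holds as a gap in the definition. Under Appendix E as written, and under Appendix F for narratives, an AE coded to a leukaemia or lymphoma term within the queries counts as a second primary even when it is the study disease or its transformation.

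The SAP does not show that any subject has been or will be misclassified, nor that the second-primary rate is overstated by any particular amount. The per-subject increments above are arithmetic on planned sizes, not evidence that such events occurred. The conclusion assumes that at least some progression or transformation events are recorded as AEs and coded to tumour terms, and that the Integrated Summary of Safety does not already resolve the matter. This is a minor point, but worth settling before lock because the correction is cheap.

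**What to change.** Keep the three queries as the search in both appendices, and add a classification step. A haematological or lymphoma hit counts as a second primary only if medical review classifies it as a new primary and not the disease under study or its transformation. The review should cover all such hits without selection and be completed and documented before database lock.

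Tabulate hits classified as transformation or progression on a separate line, so that no event is lost. In Section 12.1, align the reference to the Integrated Summary of Safety with Appendix E so that one definition governs.

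A simple exclusion of preferred terms is less safe. A term does not say whether a lymphoma is a transformation or a new primary, so the exclusion could drop a genuine new lymphoma and understate the signal.

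The cost is a few lines of text and a short medical review of what is likely to be a small number of events. Appendix F already has the medical monitor judge clinical significance for narratives outside the standard window, so this asks for no new kind of role.

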### 3. Major Hemorrhage

Major hemorrhage is defined as any hemorrhagic event that is serious, or Grade  $\geq$  3 in severity, or that is a CNS hemorrhage (any severity grade). Search Strategy:

I. Use standardized MedDRA query:

- Haemorrhage terms (excluding laboratory terms) (SMQ) [20000039]
- II. Identify Major Events that are a subset of the Haemorrhage SMQ:
  - $\circ$  Grade  $\geq 3$  AE
  - Any serious adverse event
  - All grades of CNS hemorrhage

### **CNS Hemorrhage Preferred Terms**

- Acute haemorrhagic leukoencephalitis
- Basal ganglia haematoma
- Basal ganglia haemorrhage
- Basilar artery perforation
- Brain contusion
- Brain stem haematoma
- Brain stem haemorrhage
- Brain stem microhaemorrhage
- Central nervous system haemorrhage
- Cerebellar haematoma
- Cerebellar haemorrhage
- Cerebellar microhaemorrhage
- Cerebral aneurysm perforation
- Cerebral aneurysm ruptured syphilitic
- Cerebral arteriovenous malformation haemorrhagic
- Cerebral artery perforation
- Cerebral cyst haemorrhage
- Cerebral haematoma
- Cerebral haemorrhage
- Cerebral haemorrhage foetal
- Cerebral microhaemorrhage
- Encephalitis haemorrhagic
- Epidural haemorrhage
- Extradural haematoma
- Haemorrhage intracranial
- Haemorrhagic cerebral infarction
- Haemorrhagic stroke

CONFIDENTIAL

- Haemorrhagic transformation stroke
- Intracerebral haematoma evacuation
- Intracranial haematoma
- Intracranial tumour haemorrhage
- Intraventricular haemorrhage
- Meningorrhagia
- Ocular retrobulbar haemorrhage
- Optic disc haemorrhage
- Optic nerve sheath haemorrhage
- Pituitary haemorrhage
- Putamen haemorrhage
- Retinal aneurysm rupture
- Retinal haemorrhage
- Retinopathy haemorrhagic
- Ruptured cerebral aneurysm
- Spinal cord haematoma
- Spinal cord haemorrhage
- Spinal epidural haematoma
- Spinal epidural haemorrhage
- Spinal subarachnoid haemorrhage
- Spinal subdural haematoma
- Spinal subdural haemorrhage
- Subarachnoid haematoma
- Subarachnoid haemorrhage
- Subdural haematoma
- Subdural haematoma evacuation
- Subdural haemorrhage
- Subgaleal haematoma
- Subgaleal haemorrhage
- Subretinal haematoma
- Thalamus haemorrhage
- Traumatic intracranial haematoma

Traumatic intracranial haemo

